7. ADVERSE EVENT REPORTING

7.1 Adverse Events

An *Adverse Event (AE)* is defined as

- Any new untoward medical occurrence or worsening of a pre-existing medical condition in a patient or clinical investigation participant administered an investigational (medicinal) product and that does not necessarily have a causal relationship with this treatment. An AE can therefore be any unfavorable and unintended sign (including an abnormal laboratory finding, for example), symptom, or disease temporally associated with the use of investigational product, whether or not considered related to the investigational product.
- Adverse events can be spontaneously reported or elicited during open-ended questioning, examination, or evaluation of a participant. (In order to prevent reporting bias, participants should not be questioned regarding the specific occurrence of one or more AEs.)

7.2 Serious Adverse Events

A *Serious Adverse Event (SAE)* is any untoward medical occurrence that at any dose:

- Results in death
- Is life-threatening (defined as an event in which the participant was at risk of death at the time of the event; it does not refer to an event which hypothetically might have caused death if it were more severe)
- Requires inpatient hospitalization or causes prolongation of existing hospitalization (see note below for exceptions)
- Results in persistent or significant disability/incapacity
- Is a congenital anomaly/birth defect
- Is an important medical event, defined as a medical event that may not be immediately life-threatening or result in death or hospitalization but, based on appropriate medical and scientific judgment, may jeopardize the participant or may require intervention (e.g., medical, surgical) to prevent one of the other serious outcomes listed above.
- Suspected transmission of an infectious agent (e.g., any organism, virus or infectious particle, pathogenic or non-pathogenic) via the study drug is an SAE.

If any SAE occurs the investigator will report it to the Sponsor within 24 hours of their being made aware of the SAE. Although pregnancy, overdose and cancer are not always serious by regulatory definition, these events must be handled as SAEs.

NOTE: The following hospitalizations are not considered SAEs in this study:

- A visit to the emergency room or other hospital department lasting less than 24 hours that does not result in admission (unless considered an “important medical event” or a life-threatening event)
- Elective surgery planned before signing consent
- Admissions as per protocol for a planned medical/surgical procedure

- Routine health assessment requiring admission for baseline/trending of health status (e.g., routine colonoscopy)
- Medical/surgical admission for purpose other than remedying ill health state that was planned before study entry. Appropriate documentation is required in these cases.
- Admission encountered for another life circumstance that carries no bearing on health status and requires no medical/surgical intervention (e.g., lack of housing, economic inadequacy, caregiver respite, family circumstances, administrative).

7.3 Non-Serious Adverse Events

Non-serious adverse events are all adverse events that are not classified as SAEs.

7.4 Assignment of Adverse Events

All adverse events, including those that are serious, will be graded by the investigator based on CTCAE v 4.03 as follows:

- Grade 1: Mild; asymptomatic or mild symptoms; clinical or diagnostic observations only; intervention not indicated.
- Grade 2: Moderate; minimal, local or non-invasive intervention indicated; limiting age-appropriate instrumental ADL (activities of daily living)
- Grade 3: Severe or medically significant but not immediately life threatening; hospitalization indicated; disabling, limiting self-care ADL
- Grade 4: Life threatening consequences; urgent intervention indicated
- Grade 5: Death related to AE

The following categories and definitions of causal relationship to investigational product as determined by a physician should be used:

- Related: There is a reasonable causal relationship to investigational product administration and the adverse event.
- Not Related: There is not a reasonable causal relationship between the investigational product administration and the adverse event.

The expression “reasonable causal relationship” is meant to convey in general that there are facts (e.g., evidence such as de-challenge/re-challenge) or other arguments to suggest a positive causal relationship.

7.5 Adverse Events – Collection and Reporting

Adverse events can be spontaneously reported or elicited during open-ended questioning, examination, or evaluation of a participant. To prevent reporting bias, participants should not be questioned regarding the specific occurrence of one or more adverse events.

If known, the diagnosis of the underlying illness or disorder should be recorded, rather than its individual symptoms. The following information should be captured for all AEs: onset, duration, intensity, seriousness, relationship to investigational product, action taken, and treatment required. If treatment for the event was administered, it should be recorded in the medical record.

7.5.1 Adverse Events of Special Interest

Included in the secondary outcome analysis are the adverse events of special interest (AESI). The adverse events of interest include but are not limited to:

Gastrointestinal perforations	Patients presenting with new onset abdominal symptoms should be evaluated promptly for early identification of gastrointestinal perforations and report SAE if event meets criteria.
Herpes Zoster	Though infection Herpes is a separate event of interest for this study.
Malignancy	Solid cancers, lymphoma, and non-melanoma skin cancer.
Serious Infections	Serious infections due to bacterial, mycobacterial, invasive fungal, viral, or other opportunistic pathogens. Examples of these would include: pneumonia, cellulitis, urinary tract infection, and diverticulitis, tuberculosis and other mycobacterial infections, cryptococcosis, esophageal candidiasis, pneumocystosis, multidermatomal, cytomegalovirus, and BK virus.
Lab value abnormalities compared to screening at any time point and confirmed by repeat testing	
 1. Lymphocyte count less than 500 cells/mm³ 2. ANC less than 500 cells/mm³ 3. AST/ALT >3 ULN 4. Hy's law= ALT > 3x ULN + bilirubin > 2x ULN 5. A drop of Hb by >2 gm/dL 6. Hb ≤ 8 gm/dL 7. Increase in LDL or HDL >50% 8. Increase in serum creatinine >50%

7.6 Serious Adverse Event Collection and Reporting

Following the participant's written consent to participate in the study, all AE/SAEs, whether related or not related to study drug, must be collected, including those thought to be associated with protocol-specified procedures. All SAEs must be collected that occur within 30 days of discontinuation of dosing. If applicable, SAEs must be collected that relate to any later protocol-specified procedure (e.g., a follow-up skin biopsy).

The investigator should report any SAE occurring after these time periods that is believed to be related to study drug or protocol-specified procedure.

An SAE report should be completed for any event where doubt exists regarding its status of seriousness.

If the investigator believes that an SAE is not related to study drug, but is potentially related to the conditions of the study (such as withdrawal of previous therapy, or a complication of a study procedure), the relationship should be specified in the narrative section of the SAE Report Form.

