	8.2.2 Efficacy (Activity) and Exploratory Outcomes.....	34
9	STUDY MANAGEMENT	35
9.1	Compliance with protocol.....	35
9.2	Record Retention.....	35
9.3	Study Drug Record	36
9.4	Study Drug Destruction.....	36
9.5	Study Monitoring.....	36
10	RESEARCH OF HUMAN SPECIMENS, SAMPLES OR DATA.....	37
10.1	Use of Stored Samples and Data	37
10.2	Disposition of Stored Samples and Data	37
11	REFERENCES	37

Study Synopsis

Protocol Title:	Evaluation of tofacitinib in early diffuse cutaneous systemic sclerosis (dcSSc): A phase I/II two center safety and tolerability study
Clinical Phase:	Phase I/II
Sponsor:	This is a Clinical and Research Collaborative study and [name], MS will be the sponsor. Pfizer will be supplying the drug/placebo and study funding (including drug distribution at 2 sites).
Accrual Objective:	15 subjects (10 active, 5 placebo)
Accrual Rate:	Enroll over 12 month time period
Study Duration:	Up to 65-day screening period, 24 weeks of double blind follow up, followed by 24 weeks of open label, with a 30 day follow up telephone call after permanent discontinuation of medication.
Research Centers:	2: University of Michigan and University of Pittsburgh
Research Hypothesis:	Tofacitinib is safe and is well-tolerated in patients with early dcSSc
Study Schema:	5 mg BID of tofacitinib vs placebo for 24 weeks with an open label extension receiving tofacitinib 5mg, BID for 24 weeks.
Primary Outcome:	
Primary Outcome Measure:	The primary endpoint will be the proportion of participants who experience Grade 3 or higher adverse events that occur at or before Week 24.
Secondary Outcomes:	
 • To assess the efficacy of tofacitinib in improving skin thickness in early dcSSc • To assess the efficacy of tofacitinib in improving skin and peripheral whole blood biomarkers in early dcSSc • To correlate skin and peripheral whole blood biomarkers with clinical efficacy assessments

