4. INVESTIGATIONAL PLAN

4.1 Study Design and Duration

This is a phase I/II placebo controlled study to evaluate the efficacy, safety, and tolerability, and pharmacokinetics of tofacitinib as a treatment for early dcSSc. The study will enroll approximately 15 Subjects from 18 to 70 [inclusive] years of age with active dcSSc. Subjects will be randomized to tofacitinib vs. placebo in a 2:1 ratio at 5 mg twice a day for 24 weeks. Subjects will be able to continue into the open label phase during which they will receive tofacitinib 5 mg twice a day for 24 weeks. There will be also be a follow up phone call which will occur 30 days post completing/discontinuing study medication. This study will be conducted over a period of approximately 2 years. Two sites are expected to participate in this study.

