4.8 Discontinuation of Subjects from Treatment

Subjects MUST discontinue investigational product (and non-investigational product at the discretion of the investigator) for any of the following reasons:

- Withdrawal of informed consent (participant's decision to withdraw for any reason).
- Any clinical adverse event, laboratory abnormality, or intercurrent illness which, in the opinion of the investigator, indicates that continued participation in the study is not in the best interest of the participant.
- Pregnancy
- Instruct WOCBP to contact the investigator or study staff immediately if they suspect they might be pregnant (e.g., missed or late menstrual period) at any time during study participation. Institutional policy and local regulations should determine the frequency of on-study pregnancy tests for WOCBP enrolled in the study.
- Loss of ability to freely provide consent through imprisonment or involuntary incarceration for treatment of either a psychiatric or physical (e.g., infectious disease) illness.
- Anaphylaxis or serious allergic reaction

All participants who discontinue should comply with returning to the clinic for an Early Termination visit 30 days post last dose of study drug as outlined in Section 6. For subjects whom cannot comply with returning to the clinic, then a follow up phone call should occur 30 days post last dose. The only exception to this requirement is when a participant withdraws consent for all study procedures or loses the ability to consent freely (i.e., is imprisoned or involuntarily incarcerated for the treatment of either a psychiatric or physical illness). If a participant withdraws before completing the study, the reason for withdrawal must be documented appropriately.

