6.1 Schedule of Events

The schedule of events table provides an overview of the protocol visits and procedures. Section 6 of the protocol provides detailed information on each procedure and assessment required for compliance with the protocol.

The investigator may schedule visits (unplanned visits) in addition to those listed on the schedule of events in order to conduct evaluations or assessments required to protect the well-being of the subject.

	Randomized Treatment Period						Open-Label Treatment Period				Safety FU
Study Visit Date ^a	Screening	Baseline	Week 6	Week 12	Phone Call Week 18	Week 24 ^m	Week 30	Week 36	Phone Call Week 42	Week 48	End of Study Phone Call +30d
Study Drug Dispensed											
Tofacitinib or placebo		X	X	X							
Open-label tofacitinib						X		X			
General											
Informed Consent	X										
Eligibility Review	X										
Medical History	X										
Demographics	X										
Vaccine ^p	X										
Clinical Assessments											
Physical Exam	X		X	X		X	X	X		X	
Vital Signs ^c	X	X	X	X		X	X	X		X	
Assessment of Symptoms	X	X	X	X		X	X	X		X	
mRSS ^d	X	X	X	X		X	X	X		X	
CRISS				X		X				X	
European Activity Index	X					X				X	
Physician Assessments ^e	X	X	X	X		X	X	X		X	
Patient Reported Outcomes ^f		X		X		X		X		X	
Adverse Events		X	X	X	X	X	X	X	X	X	X
Pulmonary Function Tests ^g	X			X**FVC only		X				X	
Echocardiogram w/ doppler	X					X					
Laboratory Assessments^h											
PPD/Quantiferon ⁱ	X										
ESR	X		X	X		X	X	X		X	
CRP	X					X				X	
Hepatitis B and C ^j	X										
CBC w/ diff	X	X	X	X		X	X	X		X	
Lipid Panel ⁿ	X		X				X	X			
Comp Panel	X	X	X	X		X	X	X		X	
Pregnancy Test (Urine) ^k	X	X	X	X		X	X	X		X	
Research Assessments											
Biomarkers		X	X			X					

Skin biopsy ^l		X	X								
--------------------------	--	---	---	--	--	--	--	--	--	--	--

^a Screening window will be -65 to 0 days / Remaining Visit windows will be ± 10 days

^b Follow zostervax or shingrix dosing schedule provided on page 20 of this protocol.

^c Blood pressure, Heart Rate, and Temperature. Height and Weight will also be collected at Screening visit.

^d mRSS will be assessed as one of the inclusion criterion

^e Physician Assessments include: Physician's global assessment, Tendon Friction Rub, Swollen and Tender Joint Count, Joint Contractures, and Digital Ulcer assessments.

^f Patient Reported Outcomes include: patient's global assessment, PROMIS-29 2.0, SHAQ-DI, PRO-SRSS and UCLA GIT 2.0

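### The ±10-day visit window lets the final safety contact take place on day 20, leaving up to 10 of the 30 SAE-collection days with no scheduled contact to elicit events

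*Protocol*

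**What the plan says.** Protocol 7.6 sets the collection period for serious adverse events: "All SAEs must be collected that occur within 30 days of discontinuation of dosing". Relatedness does not matter within that period. After it, the investigator is asked to report only SAEs believed to be related to study drug or a protocol procedure.

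The Schedule of Events (Protocol 6.1) ends with a safety follow-up column headed "End of Study Phone Call +30d", and the adverse event row is marked in that column. No later contact is scheduled. Footnote a, attached to the visit-date row that runs across every column, reads: "Screening window will be -65 to 0 days / Remaining Visit windows will be ± 10 days". The call has no window of its own.

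Three other places give the timing without a window. The synopsis describes the study duration "with a 30 day follow up telephone call after permanent discontinuation of medication". Section 4.1 refers to a "follow up phone call which will occur 30 days post completing/discontinuing study medication". Section 4.8 asks subjects who discontinue to comply with "returning to the clinic for an Early Termination visit 30 days post last dose of study drug"; for those who cannot come in, "then a follow up phone call should occur 30 days post last dose".

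Section 6, in stating when the skin score is collected, lists the safety call as an exception among all study visits, so the protocol's own usage counts the call as a visit.

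**The concern.** The nominal timing of the last contact and the length of the SAE period are the same, 30 days. A contact on day 30 or later can ask about the whole period; a contact before day 30 cannot. The general window allows the earlier date, and no further contact would pick up what happens next.

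Protocol 7.5 describes adverse events as either volunteered by the participant or elicited at questioning, examination or evaluation. After an early final call only the first route has any place in the schedule. The gap also falls inside the period in which all SAEs count, related or not. The primary objective is safety and there are 15 subjects, so each SAE carries weight. The independent Medical Safety Monitor (Protocol 9.5) can review only those that reach the database.

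**Working it through.** The documents give no computed figure on this point, so there is none to reproduce. The check is date arithmetic.

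**Inputs**
- SAE collection period: 30 days after the last dose (Protocol 7.6).
- Nominal final contact: day 30 (Protocol 6.1, with the anchor from 4.1 and the synopsis).
- Window: ±10 days for every visit after screening (Protocol 6.1, footnote a).
- Double-blind phase: 168 days; events starting on day 169 or later are assigned to the open-label phase (SAP, notes to Listings 3 and 5).
- Planned arms: 10 tofacitinib, 5 placebo.

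**Step 1: allowed dates.** Earliest = 30 − 10 = day 20. Latest = 30 + 10 = day 40.

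**Step 2: days without a scheduled contact.** Uncovered days = max(0, 30 − day of contact); share = uncovered days / 30.

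| Day of final contact | Uncovered days | Share of the 30 days |
|---|---|---|
| 20 | 10 | 33% |
| 24 | 6 | 20% |
| 25 | 5 | 17% |
| 28 | 2 | 7% |
| 30 to 40 | 0 | 0% |

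**Step 3: where the gap falls relative to the endpoints.** Let d be the study day of the last dose. With a day-20 contact, the uncovered days are d + 21 to d + 30.
- Subject finishing at Week 48: the gap lies after Week 48, beyond every endpoint time point.
- Subject finishing at Week 24 and not entering the open-label phase: the gap lies after Week 24, outside the primary endpoint.
- Subject stopping early: some of the gap lies at or before day 168 if d + 21 ≤ 168, that is d ≤ 147. All of it does if d + 30 ≤ 168, that is d ≤ 138.

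**Step 4: rough number of events (illustration only).** Assume the 34.1% placebo SAE proportion that Protocol 1.2.2 quotes from the tocilizumab phase 2 trial, a constant hazard, and an observation period of 24 to 48 weeks, which the protocol does not state for that figure.
- Hazard = −ln(1 − 0.341) / days = 0.417/336 = 0.00124 per day (48 weeks), or 0.417/168 = 0.00248 per day (24 weeks).
- All 15 subjects contacted on day 20: 15 × 10 = 150 uncovered subject-days, so about 0.19 to 0.37 SAEs.
- Contacts spread evenly over days 20 to 40: mean uncovered time is about 2.5 days, 15 × 2.5 = 37.5 subject-days, so about 0.05 to 0.09 SAEs.

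**Step 5: effect of one missed primary-endpoint subject.** 1/10 = 10 percentage points on tofacitinib; 1/5 = 20 points on placebo. This arises only under the early-stopper condition in step 3.

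**The case against.** The strongest reply is that nothing in 7.6 makes the call the means of collection or the end of the period. A site may call on day 25 and still record an SAE on day 28 if it hears of one. The protocol also asks for related SAEs after the period ends, when no contact is scheduled, so reporting is not tied to contacts. This stands. A reader might infer that the two rules contradict each other, but the documents do not support that: the duty runs to day 30 whatever the date of the call.

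Second, the synopsis and sections 4.1 and 4.8 say 30 days and give no window, so day 20 could be called a misreading of a general footnote about visits. This stands only in part. The footnote sits on the row that includes the call, it exempts only screening, and section 6 counts the call among the visits. If the 30-day statements are meant to be exact, the footnote needs to say so.

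Third, a reader might infer that the primary endpoint is generally exposed, with a swing of 10 or 20 points. The documents do not support that. For early stoppers the main contact in 4.8 is a clinic visit, with the call as fallback, and footnote m of the schedule brings early terminators in for the Week 24 assessments. The Early Termination visit has no column of its own, so applying ±10 days to it is an inference. A missed endpoint event would also need a Grade 3 or higher SAE in those few days, no spontaneous report, and no earlier qualifying event in that subject. For someone who stops very early, most of the unobserved time before Week 24 lies beyond day 30, which is a separate matter.

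Fourth, 33% is a worst-case share of days, not of events, and half of the window lies after day 30. This also stands.

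**Conclusion.** The concern holds as a small ascertainment gap. A compliant final contact can fall as early as day 20 and leave up to 10 of the 30 days without a scheduled opportunity to elicit SAEs. The gap is zero whenever the contact is on day 30 or later. Under the assumptions in step 4 it would contain well under one SAE across the whole trial.

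The primary endpoint is unaffected for subjects who complete the blinded phase on treatment. It could be affected only for a subject whose last dose is on or before about day 147 and whose final contact is made early, and then only if the ±10 days is taken to cover the contact in 4.8.

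The conclusion rests on reading footnote a as applying to the safety call, which is the plain reading of the schedule, and on counting the 30 days from the last dose. It is a low-priority correction, worth making because it costs almost nothing in a trial whose primary objective is safety.

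**What to change.** Reconcile footnote a with sections 7.6, 4.1 and 4.8. Add one sentence to the footnote: the minus side of the ±10-day window does not apply to the final safety contact, so that this contact cannot take place before the 30-day SAE collection period has ended. State whether the same rule covers the Early Termination visit and the fallback call in 4.8.

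The cost is one sentence in an amendment. Calls that would have been made early move back by up to 10 days, to a date the plus side of the window already allows. No contact, procedure or analysis is added, and with a contact on or after day 30 the uncovered time is 0 of 30 days. The change does not address follow-up beyond day 30 in subjects who stop early.

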7.7 Non-Serious Adverse Event Collection and Reporting

The collection of non-serious adverse event (NSAE) information should begin at initiation of study drug. NSAE information should also be collected from the start of a placebo lead-in period or other observational period intended to establish a baseline status for the participants. NSAEs should be followed to resolution or stabilization, or reported as SAEs if they become serious.

Follow-up is also required for NSAEs that cause interruption or discontinuation of study drug, or those that are present at the end of study treatment as appropriate. All identified NSAEs must be documented appropriately and reported per the sites individual local guidelines.

7.8 Laboratory Monitoring

A lab monitor will provide oversight and will review subject labs in a blinded manner. The following lab values would result in dose reduction/discontinuation of study drug:

1. Lymphocyte count less than 500 cells/mm³ and confirmed by repeat testing: discontinue drug.
2. Neutropenia. ANC 500–1000 cells/mm³: For persistent decreases in this range, interrupt dosing until ANC is greater than 1000 cells/mm³. When greater than 1000 cells/mm³, resume dose.
3. ANC less than 500 cells/mm³: discontinue drug
4. Low Hemoglobin. Greater than 2 g/dL decrease or less than 8.0 g/dL: discontinue drug until values have normalized.

